### **Diagnostic Assessments**

15 Known untreated or active central nervous system (CNS) metastases and/or carcinomatous meningitis:

- To be eligible for the study treatment, participants must have stable, well controlled disease for  $\geq$  1 month, as confirmed by magnetic resonance imaging (MRI) or CT scan, and CNS metastases must be well controlled by low dose steroids, anti-epileptics, or other symptom-relieving medications.

16 Clinically relevant proteinuria (e.g., urinary dipstick analysis for proteins is 3 + [300 mg/dL] or 4 + [1000 mg/dL], or daily urinary protein excretion  $>$  500 mg).

### **Other Exclusions**

17 Involvement in the planning and/or conduct of the study (applies to both Fusion Pharmaceuticals staff and/or staff at the study site).

18 Judgment by the Investigator that the participant should not take part in the study if the participant is unlikely to comply with study procedures, restrictions, and requirements.

19 \*Previous enrolment in the present study.

\*Note that individuals who do not meet the criteria for participation in this study (general screen failure) may be rescreened. Only one general rescreening is allowed per participant in the study. Participants who complete imaging assessment but are not eligible for treatment will not be permitted to repeat the imaging screening.

20 Currently pregnant (confirmed with positive pregnancy test) or breastfeeding.

### **5.3 Lifestyle Considerations**

The following restrictions apply while the participant is receiving study intervention and for the specified times before and after:

- Participants must follow the contraception requirements outlined in [Appendix C](#).
- Participants should not donate blood or blood components while participating in this study and through 180 days after receipt of the final dose of study intervention.
- Restrictions relating to concomitant therapies are described in [Section 6.6](#).

### **5.4 Screen Failures**

Screen failures are defined as participants who consent to participate in the clinical study but are not subsequently entered in the study. The term applies to both general screen failures and imaging screen failures. A minimal set of screen failure information is required to ensure transparent reporting of screen failure participants to meet the Consolidated Standards of Reporting Trials (CONSORT) publishing requirements and to respond to queries from regulatory authorities. Minimal information includes demography, screen failure details, eligibility criteria, and any serious adverse event (SAE). All imaging data for participants who complete imaging assessment but are not eligible for treatment must be recorded and retained as outlined in [Section 8.3](#), the Imaging Charter, and the Site Imaging Manual.

Individuals who do not meet the criteria for participation in this study (general screen failure) may be rescreened. Only one general rescreening is allowed per participant in the study. Participants who complete imaging assessment but are not eligible for treatment will not be permitted to repeat the imaging screening. Rescreened participants should be assigned the same participant number as for the initial screening.

## **6 STUDY INTERVENTION**

Study intervention is defined as any investigational intervention(s), marketed product(s) or placebo intended to be administered to or medical device(s) utilised by a study participant according to the CSP.

Please refer to the Pharmacy Manual and the IB for detailed information on the IMPs.

## 6.1 Study Intervention(s) Administered

### 6.1.1 Investigational Medicinal Products

#### 6.1.1.1 Investigational Medicinal Products Information

Please refer to the Pharmacy Manual for full details regarding the IMP preparation and administration.

#### [In]-FPI-2107 and [Ac]-FPI-2068

The [In]-FPI-2107 and [Ac]-FPI-2068 solutions for injection should be administered to the participant, undiluted, via slow (over 3 to 5 minutes) IV injection. [In]-FPI-2107 and [Ac]-FPI-2068 will be drawn up from a vial into individual syringes. The specific volume to be drawn will be calculated on the day of preparation.

No bacteriostatic agent is present in the products; therefore, adherence to aseptic technique is required. An IV tubing administration set with a 3-way stopcock is recommended during injection of [In]-FPI-2107 and [Ac]-FPI-2068 to ensure IV delivery of the products and to ensure proper priming and flushing.

The injection tubing should be primed with at least 10 mL normal saline prior to use.

[In]-FPI-2107 and [Ac]-FPI-2068 should not be diluted or administered with any other IV fluids, combined with other drugs, or administered through an injection set that was used for any purpose other than IP administration. Following injection of [In]-FPI-2107 or [Ac]-FPI-2068, the IV line should be flushed with at least 10 mL normal saline as needed to ensure delivery of the full dose. Following IP administration, the injection line should be removed from the participant and not used for any other procedures.

The radioactivity of the injection syringe before and after administration of [In]-FPI-2107 and [Ac]-FPI-2068 will be measured in the dose calibrator to determine the exact dose administered. These measurements will be recorded in the electronic case report form (eCRF).

#### FPI-2053

The FPI-2053 concentrate for infusion should be diluted in normal saline and administered to the participant via a 60-minute IV infusion. If there are interruptions, the total allowed time must not exceed 4 hours with the infusion bag kept at room temperature, otherwise a new dose must be prepared from new vials. The total time from needle puncture of the vial to the start of administration must not exceed 24 hours at 2°C to 8°C, or 4 hours at room temperature. If the final product is stored at both refrigerated and ambient temperatures, the total time must not exceed 24 hours, otherwise a new dose must be prepared from new vials. FPI-2053 does not contain preservatives; any unused portion of the vial must be discarded immediately after use.

No bacteriostatic agent is present in the product; therefore, adherence to aseptic technique is required. An IV tubing administration set with a 3-way stopcock is recommended during infusion of FPI-2053 to ensure IV delivery of the products and to ensure proper priming and flushing. Infusions must be administered through an IV administration set with a 0.2 or

0.22  $\mu$ m filter.

The infusion tubing should be primed with at least 10 mL normal saline prior to use. FPI-2053 should not be administered with any other IV fluids, combined with other drugs, or administered through an infusion set that was used for any purpose other than IP administration. Following infusion of FPI-2053, the IV line should be flushed with at least 10 mL normal saline as needed to ensure delivery of the full dose. Following IP administration, the infusion line should be removed from the participant and not used for any other procedures.

#### 6.1.1.2 Dosage

##### [In]-FPI-2107

The dose of [In]-FPI-2107 is 185 MBq (5 mCi) at the time of administration. All participants will receive the same dose of [In]-FPI-2107.

The volume to be administered to a given participant should be calculated using the:

- fixed administered dose of 185 MBq (5 mCi)
- radioactivity concentration of the product at time of calibration (the activity concentration and time and date of calibration are provided on the vial and lead pig label).

##### FPI-2053

The proposed doses of FPI-2053 are 0.3, 1, and 3 mg/kg.

The volume to be administered to a given participant should be calculated using:

- participant's body weight (kg)
- dosage level (in kBq/kg body weight)

##### [Ac]-FPI-2068

For Part A (first radiation dose level, 15 kBq/kg with and without unlabelled bsAb), dosimetry estimates of all previous and planned therapeutic administrations of [Ac]-FPI-2068 do not exceed a cumulative exposure of 23 Gy for kidneys, 31 Gy for liver, 2 Gy for red bone marrow, and 16.5 Gy for lungs. Additionally, the absorbed radiation dose to the kidneys, liver, and lungs from prior EBRT treatment must be taken into account and considered part of the cumulative dose to the organs when determining the number of cycles of treatment that a participant can receive. Eligible participants will receive up to 3 cycles of [Ac]-FPI-2068.

For Part B, dosimetry estimates of all previous and planned therapeutic administrations of [Ac]-FPI-2068 do not exceed a cumulative exposure of 23 Gy for kidneys, 31 Gy for liver, and 16.5 Gy for lungs. The absorbed radiation dose to the kidneys, liver, and lungs from prior EBRT treatment must be taken into account and considered part of the cumulative dose to the organs when determining the number of cycles of treatment that a participant can receive.

Eligible participants will receive up to 3 cycles of [Ac]-FPI-2068.

If a planned dose level exceeds the total allowable cumulative dose, the participant may receive a reduced dose.

The dose level of [Ac]-FPI-2068 will be determined by the assigned dose level (see [Table 7](#) and [Table 8](#)).

The volume to be administered to a given participant should be calculated using the:

- participant's body weight (kg)
- dosage level (in kBq/kg body weight)
- radioactivity concentration of the product at time of calibration (the activity concentration at time of calibration and the date of calibration are provided on the vial and lead pig label)

**Table 13** **Investigational Products**

Intervention name	[  In]-FPI-2107	FPI-2053	[  Ac]-FPI-2068
Type	Biologic	Biologic	Biologic
Dose formulation	Solution for injection	Concentrate for infusion	Solution for injection
Unit dose strength(s)	74–111 MBq/mL (at time of calibration)	100 mg/vial	0.407–0.629 MBq/mL (at time of calibration)
Dosage level(s)	185 MBq (5 mCi) a, b	Proposed 0.3, 1, and 3 mg/kg Q8W c	Proposed 15, 25, 40, and 70 kBq/kg Q8W b
Route of administration	IV injection	IV infusion	IV injection
Use	Experimental	Experimental	Experimental
IMP or NIMP	IMP	IMP	IMP
Sourcing	Provided centrally by the Sponsor	Provided centrally by the Sponsor	Provided centrally by the Sponsor
Packaging and labelling	Study intervention will be labelled in accordance with GMP Annex 13 and per country regulatory requirement	Study intervention will be labelled in accordance with GMP Annex 13 and per country regulatory requirement	Study intervention will be labelled in accordance with GMP Annex 13 and per country regulatory requirement
Aliases	None	None	None

GMP, Good Manufacturing Practice; IMP, investigational medicinal product; IND, investigational new drug; IV, intravenous; NIMP, non-IMP; Q8W, every 8 weeks.

a [In]-FPI-2107 is only given during the imaging screening period. All participants will receive 2 doses of [In]-FPI-2107 unless the optimal dose of FPI-2053 from Part A is 0, in which case participants in Part B will receive one dose.

b Administered dose tolerances for [In]-FPI-2107 and [Ac]-FPI-2068 are outlined in the Pharmacy Manual.

c The proposed FPI-2053 dose levels of 0.3, 1, and 3 mg/kg will be used in Part A. The FPI-2053 dose level in Part B will be determined in Part A.

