## Figure 2 Study Periods

SCREENING PERIOD		TREATMENT PERIOD		End of Treatment Period	28- or 42- (+14) Day Safety Follow Up Period	Extended Safety Follow Up Period
General Screening Period	Imaging Screening Period	CYCLE 1: 56-Day Safety Observation Period	Dosing Q56 Days	Within 7 days of decision to discontinue treatment	Resolution of Related AEs	Every 3 Months for 2 years, then every 6 months for an additional 3 years

Q56, every 56 days.

The length of each cycle within the treatment period will encompass a minimum of 56 days.

1. *General Screening Period:* All screening procedures **except baseline imaging** are to be performed during the General Screening Period. Participants must satisfy all general screening requirements (inclusion/exclusion) before undergoing baseline imaging.
2. *Imaging Screening Period:* The areas to be imaged with SPECT/CT are to be selected by the Investigator and/or appropriate delegate at the clinical sites and must include bone marrow, kidneys, lungs, and liver. [In]-FPI-2107 will be administered at a fixed dose of 185 MBq and the participant will undergo SPECT/CT imaging after administration followed by planar imaging. It is currently planned to obtain two SPECT/CT images and four planar images over approximately 5 days following administration of [In]-FPI-2107 (with or without preadministration of FPI-2053). Following completion of the general screening procedures, and confirmation of preliminary eligibility, the baseline imaging screen will be performed as follows:
  - a) **Part A:** Imaging agent [In]-FPI-2107 will be administered followed by SPECT/CT and planar imaging to be performed over 4 days. After a washout period of 6 to 8 days, participants will be administered FPI-2053, followed by [In]-FPI-2107 and will once again undergo SPECT/CT and planar imaging. The interval between the administration of FPI-2053 and [In]-FPI-2107 will be 30 minutes to 2 hours.
  - b) **Part B:** Participants will be administered FPI-2053 (at the optimal dose as defined in Part A, if applicable) followed by [In]-FPI-2107. The interval between the administration of FPI-2053 and [In]-FPI-2107 will be 30 minutes to 2 hours. The participant will then undergo SPECT/CT and planar imaging.

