**Figure 4** **Study Periods**

SCREENING PERIOD		TREATMENT PERIOD		End of Treatment Period	28- or 42- (+14) Day Safety Follow Up Period	Extended Safety Follow Up Period
General Screening Period	Imaging Screening Period	CYCLE 1: 56-Day Safety Observation Period	Dosing Q56 Days	Within 7 days of decision to discontinue treatment	Resolution of Related AEs	Every 3 Months for 2 years, then every 6 months for an additional 3 years

Q56, every 56 days.

The length of each cycle within the treatment period will encompass a minimum of 56 days.

1. *General Screening Period:* All screening procedures **except baseline imaging** are to be performed during the General Screening Period. Participants must satisfy all general screening requirements (inclusion/exclusion) before undergoing baseline imaging.
2. *Imaging Screening Period:* The areas to be imaged with SPECT/CT are to be selected by the Investigator and/or appropriate delegate at the clinical sites and must include bone marrow, kidneys, lungs, and liver. [In]-FPI-2107 will be administered at a fixed dose of 185 MBq and the participant will undergo SPECT/CT imaging after administration followed by planar imaging. It is currently planned to obtain two SPECT/CT images and four planar images over approximately 5 days following administration of [In]-FPI-2107 (with or without preadministration of FPI-2053). Following completion of the general screening procedures, and confirmation of preliminary eligibility, the baseline imaging screen will be performed as follows:
  - a) **Part A:** Imaging agent [In]-FPI-2107 will be administered followed by SPECT/CT and planar imaging to be performed over 4 days. After an appropriate washout period of 6 to 8 days, participants will be administered FPI-2053, followed by [In]-FPI-2107 and will once again undergo SPECT/CT and planar imaging. The interval between the administration of FPI-2053 and [In]-FPI-2107 will be 30 minutes to 2 hours.
  - b) **Part B:** Participants will be administered FPI-2053 (at the optimal dose as defined in Part A; if applicable) followed by [In]-FPI-2107. The interval between the administration of FPI-2053 and [In]-FPI-2107 will be 30 minutes to 2 hours. The participant will then undergo SPECT/CT and planar imaging.

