### 8.1.1 Screening Period – Part A (Dose Exploration with Unlabelled bsAb)

The SoA for the screening period in Part A is presented as two tables. **Table 17** presents the SoA from the General Screening Period until 4 days after the first [In]-FPI-2107 injection (i.e., on the day of the first dosimetry scan). **Table 18** presents the SoA from after the washout period following the first dosimetry scan until 4 days after the second [In]-FPI-2107 injection (i.e., second dosimetry scan with FPI-2053 and [In]-FPI-2107) or, if the participant does not continue in the study and does not receive [Ac]-FPI-2068, until the 28 Day Safety Visit.

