### 8.1.2 Screening Period – Part B (Hot Dose Escalation with Optimized Unlabelled bsAb)

**Table 19** Schedule of Activities – Screening Period – Part B (Hot Dose Escalation with Unlabelled bsAb)

Assessments/procedures a	General Screening D-28 to ~D-15	[  In]-FPI-2107 Imaging Screening Period							Details in Section/Appendix
		FPI-2053		[  In]- FPI-2107 Inj.	24 h (± 6 h) Post- inj. of [  In]- FPI- 2107	48 h (± 6 h) Post- inj. of [  In]- FPI- 2107	72-96 h (± 6 h) Post- inj. of [  In]- FPI- 2107		
		Pre- inj.	Inj.						
Informed consent, demographics	X								A 3
Eligibility criteria	X								5.1 & 5.2
Medical history	X								5.1 & 5.2
Concomitant medications	X	X	X	X	X	X	X	X	6.6
AE monitoring	Continuous monitoring								8.5
Haematology (whole blood)	X	X			X			X	8.4.4
Coagulation tests	X	X							8.4.4
Clinical chemistry (serum or plasma)	X	X			X			X	8.4.4
Thyroid panel	X								8.4.4
Urinalysis	X							X	8.4.4
Pregnancy test (blood or urine in accordance with institutional practice)	X	X						X	8.4.4
Complete physical examination	X							X	8.4.1
Symptom-directed physical		X		X	X				8.4.1

Assessments/procedures a	General Screening D-28 to ~D-15	[  In]-FPI-2107 Imaging Screening Period							Details in Section/Appendix	
		FPI-2053		[  In]- FPI-2107 Inj.	24 h (± 6 h) Post- inj. of [  In]- FPI- 2107	48 h (± 6 h) Post- inj. of [  In]- FPI- 2107	72-96 h (± 6 h) Post- inj. of [  In]- FPI- 2107	28-Day Safety Visit b		
		Pre- inj.	Inj.							
examination										
ECOG Performance Status	X							X	8.4.5	
Height	X								8.4.1	
Weight	X	X							8.4.1	
Vital signs	X	X		X c	X	X		X	8.4.2	
Ophthalmologic examination	X								8.4.6.2	
ECG (12-lead)	Table 27								8.4.3	
FPI-2053 administration			X						6.1	
[  In]-FPI-2107 administration				X					6.1	
Whole body planar scintigraphy d				X					8.3.2	
SPECT/CT imaging e, f					X				8.3.1	

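### Table 13 implies two imaging doses in Part B when a non-zero FPI-2053 dose is carried forward, but the synopsis, Section 4.1.4 and the Part B schedules provide for one

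*Protocol*

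**What the plan says.** Footnote a to Table 13 (Section 6.1.1.2) sets a general rule, "All participants will receive 2 doses of" the imaging agent, and one exception: "unless the optimal dose of FPI-2053 from Part A is 0, in which case participants in Part B will receive one dose".

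The design text treats the two parts differently. For Part A the synopsis describes imaging with the agent alone and then a second round: "After a washout period of 6 to 8 days, participants will be administered FPI-2053, followed by" the imaging agent. For Part B the synopsis has one step: "Participants will be administered FPI-2053 (at the optimal dose as defined in Part A, if applicable) followed by" the imaging agent. Section 4.1.4 repeats this, "Participants will be administered FPI-2053 (at the optimal dose as defined in Part A; if applicable) followed by" the agent, and closes the step with "The participant will then undergo SPECT/CT and planar imaging". Neither place mentions a second administration in Part B.

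The schedules follow the design text. Section 8.1.1 says of Part A: "The SoA for the screening period in Part A is presented as two tables", and Tables 17 and 18 have one injection each. Table 19, for Part B with FPI-2053, has one injection column. Table 26 (Part A) has two imaging blocks of PK and ECG timepoints. Table 27 (Part B with FPI-2053) has one.

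**The concern.** The exception in the footnote names Part B, so the general rule cannot be read as covering Part A alone. Read as written, a non-zero optimal FPI-2053 dose leaves Part B under the two-dose rule, and four other places in the same protocol contradict that.

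The subject is the number of radioactive administrations, and the conflict sits in the table that defines the products and their dosage. Section 6.5 treats doses above those specified in the protocol as overdose, and Section 8 allows no waivers and requires adherence to the schedules. With two counts in force, a site that complies with one departs from the other. The footnote also does not say whether a second Part B dose would be given alone or after FPI-2053, so even a site wishing to follow it would lack an instruction.

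**Working it through.** No power or error-rate calculation applies. The check is a count of imaging administrations in each place, multiplied by the dose per administration.

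**Inputs.** Activity per administration is 185 MBq (Section 6.1.1.2). Protein per administration is up to 5 mg (Section 4.3.1).

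**Count by setting.**

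| Setting | Table 13 footnote a | Design text and schedules | Agree? |
|---|---|---|---|
| Part A | 2 | 2 (Tables 17 and 18; two blocks in Table 26) | Yes |
| Part B, hot-only | 1 | 1 (Table 20; one block in Table 28) | Yes |
| Part B with FPI-2053 | 2 | 1 (synopsis; Section 4.1.4; Table 19; one block in Table 27) | No |

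**Size per participant in Part B with FPI-2053.**

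- Footnote: 2 × 185 = 370 MBq; 2 × 5 = up to 10 mg protein.
- Design text and schedules: 1 × 185 = 185 MBq; 1 × 5 = up to 5 mg protein.
- Ratio: 370 / 185 = 2.

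**Calendar check.** General screening runs from D-39 to about D-26 in Part A (Table 17) and from D-28 to about D-15 in Part B (Table 19). Both ends differ by 11 days (39 − 28 and 26 − 15). If the Part A washout is counted from the end of imaging, an extra imaging round takes 4 + 6 = 10 to 4 + 8 = 12 days. The 11-day shift therefore matches one extra round in Part A and none in Part B.

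Two rounds in Part B, followed by the 14 to 17 day washout before treatment, would need 10 + 14 = 24 to 12 + 17 = 29 days. A participant who finishes general screening near D-15 has about 15 days. One who finishes near D-28 has about 28. Two rounds therefore do not fit the usual course of the Part B schedule, but the window does not strictly exclude them.

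**The case against.** The best defence is that the footnote stands alone. The synopsis, Section 4.1.4, Table 19 and Table 27 all agree, Section 8 makes adherence to the schedules mandatory, and Part B offers a site no column, visit or sampling row in which to give a second dose. On this view the practical risk is small. That stands as a limit on the likely consequences. It does not remove the contradiction: the footnote is current text, and it addresses Part B explicitly.

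Three stronger readings are tempting, and the documents do not support them.

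- **A head count of about 98 of 107 participants.** Section 4.1 plans 18 + 20 + 60 = 98 participants after Part A, and 98 + 9 = 107 in all. These figures describe planned enrolment, whereas the imaging agent is given during screening and so also reaches imaging screen failures. Section 9.2 plans about 125 safety-evaluable participants, and Table 30 defines the safety set by any receipt of the imaging agent. Section 4.1.1 allows one or two backfill levels of about 20 each. If the optimal dose is 0, the number is zero. So 98 is neither the imaged population nor a bound on it.
- **No room and no safety cover for a second dose.** The window makes a second round unlikely, not impossible. Table 19 does contain continuous adverse event monitoring and a 28-day safety visit for participants imaged but not treated. What is missing is any visit or sample timed around a second administration.
- **An undefined primary dosimetry comparison.** The endpoint in Section 3 compares imaging after predosing with imaging alone. Only Part A schedules both conditions, and its stated purpose is to find the optimal predose. Naming the contributing part would be a useful clarification, but its absence is not an error.

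**Conclusion.** The contradiction holds, in one setting only: Part B with a non-zero FPI-2053 dose carried forward from Part A. There the product table implies two imaging administrations and the rest of the protocol schedules one, a two-fold difference in administered imaging activity and in the upper limit on protein mass from the imaging agent. The number of participants affected depends on the outcome of Part A. It is none if the optimal dose is 0, and otherwise everyone imaged under the Part B schedule with FPI-2053.

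This rests on reading the footnote's exception as exhaustive, which its wording supports, and on the schedules being complete as shown. It is an inconsistent dosing rule that should be corrected. It is not evidence that anyone has received or will receive an extra dose.

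**What to change.** Reconcile footnote a of Table 13 with the Part B imaging step in the synopsis and Section 4.1.4, and with Tables 19 and 27, so that the number of imaging administrations in Part B with FPI-2053 is the same everywhere. Which number is right is for the sponsor to decide.

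The cost depends on that decision. If the schedules stand, one footnote changes. If the footnote stands, the synopsis, Section 4.1.4, Table 19 and Table 27 need a second imaging round with its own visits, samples and timing, the condition of each dose (alone or after FPI-2053) must be stated, and the Part B screening window must be rechecked. Either change can go into the next amendment.
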